4.5 Exploratory Effectiveness Endpoints

The following exploratory effectiveness endpoints will be evaluated for eyes that achieve ≥ 20 letters of improvement in UCNVA during preoperative simulation testing.

- Proportion of eyes (≥ 75%) achieving improved reading speed (at 40 cm) at 12 months from baseline defined as ≥ 2 lines/blocks of gain with a decrease in reading speed ≥ 1 minute and with overall improvement in critical point size
- Proportion of eyes (≥ 75%) achieving independence from external magnifier usage at 12 months postoperatively.

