15. CLINICAL ASSESSMENTS

All parameters will be recorded for both eyes at baseline (pre-operative). Measurements will be recorded for the study eye at postoperative and post-removal visits. See Appendix 2A schedule of visits (pre- and post-operative visits) and Appendix 2B (post-removal visits). See Appendix 3 for clinical assessment instructions.

Order of Clinical Assessments:

- Mesopic contrast sensitivity testing should be performed prior to the slit lamp examination
 and before any visual acuity testing that requires bright light directed at the subject (i.e., a
 reading lamp shined directly over the subject's shoulder onto the reading card).
- Confirmation of IOPCL location should be performed after the study eye is dilated.

Study sites are expected to implement COVID-19 pandemic safety measures in accordance with their local, state, and CDC health guidelines to ensure the health and well-being of the subjects and study staff who come in contact with the subjects.

Clinical Assessments and Timepoints

- Inclusion/exclusion criteria: Preoperative
- Medical history: Preoperative
- External magnifier usage: Preoperative, 30-60 days, 120-180 days, 330-420 days. Interim
 - Post-removal, 30-60 days, 120-180 days, 330-420 days, Interim
- Demographics: Preoperative
- Patient Informed Consent: Preoperative
- Capsulorhexis Size at the time of PCIOL surgery: Preoperative
- Position of PCIOL Haptics and Planned IOPCL Incision Location: Preoperative
- Axial Length: Preoperative
- Keratometry: Preoperative

- Mesopic and Photopic Pupil size measured by Pupillometer: Preoperative.
- Pseudophakic PCIOL power with make and model number: Preoperative.
- Simulation of expected outcome (3.0D lens over manifest refraction at 30cm and 7.0D lens over manifest refraction, at 14cm and preferred distance): Preoperative.
- Ocular Dominance: Preoperative
- Optical Coherence Tomography: Preoperative, 30-60 days, 120-180 days, 330-420 days.
 Interim
 - Post-removal, 30-60 days, 120-180 days, 330-420 days, Interim
- Capsular Stability: Preoperative, Operative, 7-14 days, 30-60 days, 120-180 days, 330-420 days, Interim
 - Post-removal, 7-14 days, 30-60 days, 120-180 days, 330-420 days, Interim
- Spatial Visualization between the PCIOL and IOPCL Using UBM: 30-60 days, 120-180 days, 330-420 days, Interim.
- Recording of the IOPCL Surgical Procedure: Operative
- IOPCL Location and Confirmation of Incision Location: Operative

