- IOPCL Location (following dilation): 1-2 days, 7-14 days, 30-60 days, 120-180 days, 330-420 days, Interim
- Manifest Refraction: Preoperative, 7-14 days, 30-60 days, 120-180 days, 330-420 days, Interim
 - Post-removal, 7-14 days, 30-60 days, 120-180 days, 330-420 days, Interim
- Add Power: Pre-Operative, 7-14 days, 30-60 days, 120-180 days, 330-420 days, Interim.
 - Post-removal, 7-14 days, 30-60 days, 120-180 days, 330-420 days, Interim
- BCDVA: Best Corrected Distance Visual Acuity (at 6m) Preoperative, 7-14 days, 30-60 days, 120-18 days, 330-420 days, Interim
 - Post-removal, 7-14 days, 30-60 days, 120-180 days, 330-420 days, Interim
- BCNVA: Best Corrected Near Visual Acuity (at 30 cm (preoperatively); 14 cm (postoperatively) and preferred reading distance (preoperatively and postoperatively)) Pre-Operative, 7-14 days, 30-60 days, 120-180 days, 330-420 days, Interim.
 - Post-removal, 7-14 days, 30-60 days, 120-180 days, 330-420 days, Interim

- UCDVA: Uncorrected Distance Visual Acuity (at 6m)— Preoperative, 7-14 days, 30-60 days, 120-180 days, 330-420 days.
 - Post-removal, 7-14 days, 30-60 days, 120-180 days, 330-420 days. Interim
- UCNVA: Uncorrected Near Visual Acuity (at 14 cm and preferred reading distance) –
 Preoperative, 7-14 days, 30-60 days, 120-180 days, 330-420 days
 - Post-removal, 7-14 days, 30-60 days, 120-180 days, 330-420 days, Interim
- Central Visual Field (Amsler Grid): Preoperative
- Reading Speed (Smith-Kettlewell testing at 40 cm): Preoperative, 7-14 days, 30-60 days, 120-180 days, 330-420 days
 - Post-removal, 7-14 days, 30-60 days, 120-180 days, 330-420 days, Interim
- Contrast Sensitivity (Mesopic): Preoperative, 7-14 days, 30-60 days, 120-180 days, 330-420 days
 - Post-removal, 7-14 days, 30-60 days, 120-180 days, 330-420 days, Interim
- Slit Lamp Examination: Preoperative, 1-2 days, 7-14 days, 30-60 days, 120-180 days, 330-420 days, Interim.
 - Post-removal, 1-2 days, 7-14 days, 30-60 days, 120-180 days, 330-420 days, Interim
- Gonioscopy: 7-14 days, 30-60 days, 120-180 days, 330-420 days, Interim
 - Post-removal, 7-14 days, 30-60 days, 120-180 days, 330-420 days, Interim
- Intraocular Pressure: Preoperative, 1-2 days, 7-14 days, 30-60 days, 120-180 days, 330-420 days, Interim
 - Post-removal, 1-2 days, 7-14 days, 30-60 days, 120-180 days, 330-420 days, Interim
- Dilated Fundoscopy: Preoperative, 7-14 days, 30-60 days, 120-180 days, 330-420 days, Interim

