# 3.1.3 Exploratory Effectiveness Endpoints

The following exploratory effectiveness endpoints evaluated for eyes that achieve  $\geq 20$  letters of improvement in UCNVA during preoperative simulation testing.

- Proportion of eyes (≥ 75%) achieving improved reading speed (at 40 cm) at 12 months from baseline defined as ≥ 2 lines/blocks of gain with a decrease in reading speed ≥ 1 minute and with overall improvement in critical point size
- Proportion of eyes (≥ 75%) achieving independence from external magnifier usage at 12 months postoperatively

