## 7.4.3 Exploratory Effectiveness Endpoints

The following exploratory effectiveness endpoints will be evaluated for eyes that achieve  $\geq 20$  letters of improvement in UCNVA during preoperative simulation testing.

• Proportion of eyes (≥ 75%) achieving improved reading speed (at 40 cm) at 12 months from baseline defined as ≥ 2 lines/blocks of gain with a decrease in reading speed ≥ 1 minute and with overall improvement in critical point size

Change in reading speed will be reported as follows:

- Change in lines/blocks using the following bins: loss of 3 or more blocks, loss of 2 or more blocks, loss of more than 1 block, no change (within 1 block), gain of more than 1 block, gain of 2 or more blocks, gain of 3 or more blocks, gain of 4 or more blocks.
- Change in reading rate using the following bins: loss of 3 minutes or more, loss of 2 or more minutes, loss of more than 1 minute, no change (within 1 minute), gain of more than 1 minute, gain of 2 or more minutes, gain of 3 or more minutes, gain of 4 or more minutes.
- Change in critical point size using the following bins: loss of 3 or more point sizes, loss of 2 or more point sizes, loss of 1 point size, no change in point size, gain of 1 point size, gain of 2 or more point sizes, gain of 3 or more point sizes, gain of 4 or more point sizes.

Reading speed of the primary eyes will be summarized descriptively by mean, standard deviation, median, minimum, and maximum at 1 month or later.

• Proportion of eyes (≥ 75%) achieving independence from external magnifier usage at 12 months postoperatively

Independence from external magnifier usage will be reported using the following bins: continued usage of all external magnifier(s) used preoperatively (no change), deceased usage of 1 or more external magnifiers used preoperatively (partial independence); deceased usage of all external magnifiers used preoperatively (complete independence)

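### The exploratory reading endpoint scores speed as an absolute saving of minutes, so some eyes that read faster can be counted as failures

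*Protocol*

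**What the plan says.** Protocol 4.5 sets a target of at least 75% of eyes with improved reading speed at 12 months, "defined as ≥ 2 lines/blocks of gain with a decrease in reading speed ≥ 1 minute and with overall improvement in critical point size". SAP 3.1.3 and 7.4.3 repeat the definition. An eye must meet all three conditions. Only eyes that gained at least 20 letters in the preoperative simulation are evaluated.

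SAP 7.4.3 then reports the components one by one. For speed it specifies "Change in reading rate using the following bins: loss of 3 minutes or more", running up to gains of 4 minutes or more, with a middle category for changes within 1 minute. Blocks have their own bins ("Change in lines/blocks using the following bins: loss of 3 or more blocks", and so on), as does critical point size. Reading speed is also to be summarised by mean, SD, median, minimum and maximum, with no unit given.

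Protocol 15 names the test as Smith-Kettlewell at 40 cm and sends the reader elsewhere for method: "See Appendix 3 for clinical assessment instructions". That appendix is not in the text available for review. The available text does not say whether the minutes are total time over all blocks read, time per block, or time on text read at both visits. It defines no words-per-minute measure.

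**The concern.** A saving of one minute is a change in duration. It equals a given change in speed only when the amount of text and the baseline time are fixed, and neither is. Whether an eye passes therefore depends partly on how long its baseline test took. The same sentence also asks for at least 2 more blocks. If time is summed over everything read, that extra text adds minutes to the follow-up test.

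This is the only responder endpoint in Protocol 4.3 to 4.5 built on the reading test; the others use letters or magnifier use. A feasibility study should help choose endpoints for later work, and a criterion that can miss real gains in speed is a weak guide. The minute bins carry the same problem into the descriptive tables.

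Taken literally, a decrease in speed is a worsening, and the SAP does not say which direction its loss and gain bins refer to. The working below takes the favourable sense, that reading time falls.

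**Working it through.** The plan gives no expected value, power or sample-size derivation for this endpoint, so there is no figure to reproduce.

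**Inputs from the documents:** at least 2 blocks gained, a change of at least 1 minute, a 75% target, and at most 10 eyes (SAP 6.2).

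**Assumed, because the documents give neither:** baseline time T0 (minutes) and, for total-time scoring, baseline blocks B with equal text per block. Both are shown over a range. Let k be 12-month speed divided by baseline speed, and T1 the 12-month time. The time condition is T0 − T1 ≥ 1.

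**Step 1, the floor.** T1 is above zero, so the saving is always less than T0. If T0 ≤ 1 the condition cannot be met at any k. This holds for total, per-block or common-text time. If time is per block, with an assumed 12 words per block (range 8 to 20), only eyes reading below 12 words per minute at baseline (8 to 20) could pass.

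**Step 2, time on common text.** T1 = T0/k, so k ≥ T0/(T0 − 1).

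**Step 3, total time over all blocks read, 2 blocks gained.** T1 = T0 × (B + 2)/(B × k), so k ≥ [(B + 2)/B] × T0/(T0 − 1).

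Speed-up needed to pass:

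| T0 (min) | Common text | Total time, B = 4 | Total time, B = 6 | Total time, B = 8 |
|---|---|---|---|---|
| 1 or less | impossible | impossible | impossible | impossible |
| 1.5 | 3.00 | 4.50 | 4.00 | 3.75 |
| 2 | 2.00 | 3.00 | 2.67 | 2.50 |
| 3 | 1.50 | 2.25 | 2.00 | 1.88 |
| 5 | 1.25 | 1.88 | 1.67 | 1.56 |
| 10 | 1.11 | 1.67 | 1.48 | 1.39 |

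**Step 4, examples.**
- 4 blocks in 3 minutes, then 6 blocks at double speed. Total time: T1 = 3 × 6/(4 × 2) = 2.25, a saving of 0.75, so the eye fails. Common text: T1 = 3/2 = 1.5, a saving of 1.5, so the same eye passes.
- 8 blocks in 10 minutes, then 10 blocks at 1.5 times the speed. Total time: T1 = 10 × 10/(8 × 1.5) = 8.33, a saving of 1.67, so the eye passes.
- Speed doubled, total time: the condition becomes T0 × [1 − (B + 2)/(2B)] ≥ 1. At B = 2 the bracket is 0 and no eye passes. At B = 4 it is 0.25, so T0 must be at least 4 minutes. At B = 6 it is 1/3, so T0 must be at least 3 minutes.

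**Step 5, tabulation.** The 0.75-minute saving falls in the SAP's middle bin, so under total-time scoring a doubled rate would be listed as unchanged.

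**Step 6, the target.** 75% means 8 of 10 eyes (7.5 rounded up), 6 of 8, or 4 of 5 (3.75 rounded up). One or two misclassified eyes can move the result across the mark.

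**The case against.** The best reply is that the documents do not say what is timed. A reader might infer that the block and minute conditions always oppose each other, so that faster eyes fail as a rule. The available text does not support that. The opposition needs total time over all blocks; with per-block or common-text timing it disappears. Even under total time, eyes with long baselines or large speed-ups pass. Baseline acuity runs from 20/80 to 20/800 (Protocol 5.1), so long baseline times are plausible, though none are given. This part of the objection stands, and the conflict is stated here only as conditional.

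A reader might also infer that eyes with the least baseline reading are shut out. That confuses few blocks with short time: for a given number of blocks, a slower reader has a longer baseline and passes more easily. For an eye that reads no block at baseline, the documents do not say how time is scored, so its result is undefined and not a proven failure.

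Finally, a reader might expect a low proportion to be taken as no functional benefit. The SAP reports blocks and critical point size separately, plans a descriptive summary of reading speed, and has magnifier use and the VFQ-25 as further evidence. No test or decision rule is attached to the endpoint. That limits the harm. It does not repair the minute bins, and the reading-speed summary has no unit.

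The floor at 1 minute is untouched by any of these points.

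**Conclusion.** The point holds in a limited form. The criterion and the SAP bins express speed as minutes, and an absolute one-minute saving is out of reach for any eye with a baseline time of 1 minute or less, however time is counted. Just above that floor the demand is steep: 3.0 times at 1.5 minutes and 2.0 times at 2 minutes, even on common text. If total time is used, the block gain raises the bar by a further factor of (B + 2)/B, which is 1.5 at B = 4 and 1.25 at B = 8.

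Some eyes that read faster can therefore be scored as failures or listed as unchanged. How many cannot be said, because the documents give no baseline times. The results rest on the favourable reading of the time condition, on the assumed ranges for T0 and B and, for the block conflict, on total-time scoring. The endpoint is exploratory and descriptive, in a subset of at most 10 eyes, so this is a definition worth correcting before lock and not a threat to the study's main conclusions.

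**What to change.** In Protocol 4.5 and SAP 3.1.3 and 7.4.3:

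- Replace the minute condition with an increase in reading rate, in words (or amount of text) per minute, and state that higher is better. Where time is recorded by block, compute the rate on blocks read at both visits. Otherwise use total text read divided by total time.
- Express the change as the 12-month to baseline ratio, and fix the minimum ratio before database lock.
- Replace the minute bins in SAP 7.4.3 with change in rate, and give the descriptive summary of reading speed the same unit.
- State how eyes that read no block at baseline are handled, and report them separately, so that one proportion does not mix two success rules.

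On total text over total time, the 4-block, 3-minute eye goes from 4/3 = 1.33 to 6/2.25 = 2.67 blocks per minute. That is a ratio of 2.0, which is its true speed-up.

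The cost is wording in two documents and the choice of a minimum ratio. No visit or test is added. The common-block version needs time kept by block; the case report forms and Appendix 3 are not in the available text, so whether that is already recorded has to be checked. If it is not, the total-text version still removes the problem with the unit.

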5. SUBJECT POPULATION

A maximum of 10 pseudophakic eyes in subjects with a diagnosis of age-related macular degeneration will be implanted unilaterally with the IOPCL AMD-MAG. All ocular eligibility criteria refer to the study eye only.

5.1. Inclusion Criteria

- 1. Subjects aged 55 years or older.
- 2. Subjects who have already had cataract surgery with an Alcon SN60WF, SA60AT or SA60WF monofocal intraocular lens with a lens power between 17.0 diopters and 24.0 diopters clearly evidenced by photographic documentation by one of the following:
 - patient medical record
 - clinic chart with labeling attached
 - surgical record with labeling attached, or
 - patient identification card with make, model and serial number.
- 3. Subjects who have already had cataract surgery at least 6 months from the planned date of the IOPCL surgery.
- 4. Subjects with non-neovascular dry AMD or stable wet AMD meeting the following criteria:
 - No macular fluid retention in the past 12 months
 - No treatment within the past 12 months
 - No change in Amsler Grid test within the past 12 months
 - No subretinal fluid or macular hemorrhage confirmed by optical coherence tomography (OCT) imaging.
 - No fundoscopic changes within the past 12 months (i.e., changes in retinal pigment epithelium).
- 5. Subjects with best corrected distance visual acuity from 20/80 to 20/800.
- 6. Subjects with a preoperative manifest refraction spherical equivalent (MRSE) of +1.0D to -1.0D.
- 7. Subjects with ≤1.0D of corneal cylinder determined by keratometry readings.
- 8. Subjects who are unsatisfied with their current near vision correction provided by either spectacles or external magnifier.
- 9. Subjects who have experienced and failed one or more high-magnification refractive correction alternatives to the IOPCL AMD-MAG.

- 10. Subjects who demonstrate at least 10 letters of near visual acuity improvement with the simulation/tolerance test (using manifest refraction with +7.0D add) compared to conventional near vision testing (using manifest refraction with +3.0D add).
- 11. Subjects with a minimum endothelial cell count of 1800 cells/mm².
- 12. Subjects willing to abstain from pursuing any other surgical vision-correcting procedures for the duration of the study.
- 13. Subjects who are willing and able to complete all required postoperative visits.
- 14. Subjects who are able to comprehend and sign a statement of informed consent.

5.2. Exclusion Criteria

- 1. Subjects who have already had cataract surgery with a toric or multifocal or accommodating Intraocular Lens.
- 2. Subjects who have already had cataract surgery with an Alcon SN60WF, SA60AT or SA60WF monofocal intraocular lens with a power below 17.0 diopters and greater than 24.0 diopters.
- 3. Subjects with non-stable neovascular (wet) AMD who received treatment within the past 12-months.
- 4. Subjects who have had a Nd: YAG capsulotomy less than 1 month prior to the planned date of the IOPCL surgery.
 - 5. Subjects who were treated with an PCIOL off-label.
 - 6. Subjects who have more than 1.0D of corneal cylinder determined by keratometry readings.
 - 7. Subjects whose continuous curvilinear capsulorhexis was less than 5mm or more than 6.0 mm in size at the time of PCIOL surgery.
 - 8. Subjects who had cataract surgery less than 6 months from the planned date of the IOPCL surgery.
 - 9. Subjects with anterior capsule fibrosis and phimosis that in the opinion of the investigator may confound the outcome or increase the risk to the subject.
 - 10. Subjects with capsular instability.
 - 11. Subjects with an anterior capsule defect.
 - 12. Subjects with posterior capsular defect (caused by Nd:YAG capsulotomy) extending toward the equator.
 - 13. Subjects who do not gain at least 10 letters of near visual acuity with the simulation/tolerance testing (using manifest refraction with +7.0D add) compared to conventional near vision testing (using manifest refraction with +3.0D add).
 - 14. Subjects with a concomitant retinal or choroidal disorder other than AMD.
 - 15. Subjects with any corneal abnormality, other than regular corneal astigmatism that in the opinion of the investigator would confound the outcome(s) of the study.
 - 16. Subjects with clinically severe corneal dystrophy (e.g., epithelial, stromal, or endothelial dystrophy).

- 17. Subjects with microphthalmos.
- 18. Subjects with a previous retinal detachment.
- 19. Subjects with a recurrent severe anterior or posterior segment inflammation of unknown etiology.
- 20. Subjects with iris neovascularization.
- 21. Subjects with glaucoma.
- 22. Subjects with advanced visual field defects (e.g., central large scotoma where magnification would not help).
- 23. Subjects with a fundus not visible.
- 24. Subjects with aniridia.
- 25. Subjects with advanced optic nerve atrophy.
- 26. Subjects with damaged or incomplete zonules.
- 27. Subjects with a known history of pseudoexfoliation.
- 28. Subjects with acute, chronic or uncontrolled systemic or ocular disease that in the opinion of the investigator would increase the operative risk or confound the outcome(s) of the study.
- 29. Subjects with medications that, in the opinion of the investigator, may confound the outcome or increase the risk to the subject (tamsulosin hydrochloride (Flomax)) or other medications with similar side effects (floppy iris syndrome).
- 30. Subjects with cognitive impairment that may interfere with the ability to understand the potentially complex considerations underlying an informed decision on trial participation and/or interfere with the ability to neuro-adapt to this device in the postoperative period.

6. SUBJECT ENTRY

The investigator or qualified site personnel will explain the study purpose and procedures necessary to allow the subject to decide whether to give informed consent and will explain the subject's responsibilities (see Appendix 1).

The subject's willingness and ability to meet the follow-up requirements will be determined. After it has been determined that all inclusion/exclusion criteria have been met the subject will be enrolled into the study.

6.1. Outcome Simulation Testing

After informed consent has been obtained the subject will be required to participate in a "Outcome Simulation test." First, the subject's manifest refraction will be placed in a trial frame. Next, using the add power of commonly-used spectacles, a +3.0D lens will be placed into the trial frame and near visual acuity will be tested using the Sloan Near Vision Chart at 30 centimeters (11.5 inches) and at the subject's preferred reading distance (i.e., the distance at which the subject can most clearly see the chart or reading material). Then, the +3.0D lens will be exchanged for a +7.0D lens and near visual acuity will be assessed using the Sloan chart at 14 centimeters (5.5 inches) and the

subject's preferred reading distance. This will closely simulate the expected outcome after surgery and determine if he/she can tolerate the high magnification. Subjects who demonstrate at least 10 letters of near visual acuity improvement with the +7.0D lens, compared to near visual acuity achieved with the +3.0D lens, will have the option to continue with the remaining pre-operative testing or to withdraw from the study. Subjects who fail to achieve at least 10 letters of near visual acuity improvement with the simulation testing or who are not completely tolerant of their vision during the simulation testing will be exited from the study.

